1.2.3.2 Pharmacokinetics of Temsirolimus plus Sorafenib in Combination

In the phase I study of temsirolimus and sorafenib discussed above, preliminary results suggested that sorafenib may increase levels of the temsirolimus metabolite, rapamycin

(sirolimus), at steady state, though there were no other drug-drug interactions observed.(Patnaik A 2007) Sorafenib exposure was similar at dosages of both 200 mg and 400 mg twice daily in this study. The phase I drug interaction study evaluating the combination of sirolimus and sorafenib discussed above showed no significant interactions observed.(Gangadhar, Cohen et al. 2011) Likewise, the available data suggests no clinically relevant, measurable pharmacokinetic interaction between everolimus and sorafenib in two phase I studies of this combination in RCC (both drugs) and HCC (everolimus only).(Finn 2011; Harzstark, Small et al. 2011) Pharmacokinetic analyses for temsirolimus and its primary metabolite, sirolimus, from the UCSF-Northwestern phase I trial of temsirolimus plus sorafenib in HCC showed peak drug concentration (C_{max}) for temsirolimus was similar before and after addition of sorafenib, while that of sirolimus was nonsignificantly increased. (Kelley 2012) Clearance of temsirolimus was more rapid after addition of sorafenib (5.86 L/h vs 4.37 L/h, statistical t-test, $p < 0.05$), with a nonsignificant decrease in temsirolimus half-life. The AUC inf for temsirolimus was significantly lower (statistical t-test, $p < 0.05$) after addition of sorafenib, while there was a nonsignificant trend towards increase in C_{max} and AUC inf for sirolimus. There was significant interpatient variability for sirolimus across timepoints. Compared to healthy volunteers and cancer patients without liver dysfunction who were treated with 25 mg dose of temsirolimus, the C_{max} for both temsirolimus and sirolimus was lower in this study which utilized a 10 mg dose.(Sarantopoulos 2011) The AUC of single-agent temsirolimus prior to addition of sorafenib in this cohort appeared similar to the non-HCC subjects treated at the 25 mg dose, and clearance was slower.

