9.2.2 Accrual estimates

It is estimated that 12 patients will be accrued annually (approximately 1 patient per month) combined between UCSF and Northwestern. This estimate is based upon the accrual to the predecessor Phase I study of this combination which enrolled 25 patients with similar eligibility criteria between December 2009 and April 2012. It is expected that the Phase II study will accrue faster than the Phase I due to the established infrastructure and momentum from the Phase I study, along with no requirement for delays for dose escalation and frequent amendments which were associated with the Phase I study.

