9.4.4 Exploratory Analyses/Assessments

- CTC levels: Baseline level of CTC (detectable or undetectable) will be compared to proportion with TTP at 6 months to determine if there is an association using Fisher's Exact tests. Change in CTC levels (increase or decrease) after 1 and 2 cycles will be compared to proportion with TTP at 6 months to determine if there is an association using Fisher's Exact tests. Markers of mTOR pathway activation: Descriptive statistics will summarize the IHC parameters of staining intensity, percentage positivity, distribution, and intracellular localization for each protein. Due to possible limited specimen quantity, IHC outcomes will be dichotomized. Activation will be measured by % positive cells and intensity using published IHC cutpoints for high/low: cytoplasmic pAkt > 40% or 2-3+, cytoplasmic PTEN intensity < 10% or 0-1+, cytoplasmic pS6RP > 70% or 2-3+, or LKB1 0-1.⁷⁻¹² Univariate analysis using Cox's model will be performed to test whether the dichotomized expression of each protein using the published cutpoints is a significant predictor of TTP. Results for each test will include the hazard ratio (HR) with 95% confidence intervals. The association between each protein and the two binary coding schemes for AFP decline ($\geq 50\%$ or $\geq 20\%$) on C2D1 will be tested using Fisher's exact test. Results for each test will be summarized with proportions with pathway activation and 95% confidence intervals for each AFP subset. Each patient will also be categorized as having overall mTOR pathway activation (defined as any combination of high pAKT, high pS6RP, low PTEN, and/or low LKB1) or not. This binary variable will also be examined for its relationship with TTP, OS, AFP response, and other clinical endpoints using the same methods described above. For each test of association with AFP change, based upon Fisher's exact test large differences can be detected (e.g. 10% among 7 patients with marker-low, 80% among 8 patients with marker-low) (power=81%, $\alpha_2=10\%$). The sample size is too small to test for a difference in TTP, OS, or other clinical endpoints according to pathway activation status. The expected sample size will be ≥ 25 cases (expect 40 to 45 cases) with IHC-quality archival tumor, with the expectation that $\sim 75\%$ of cases will be evaluable for TTP ($n \geq 18$) and 60% evaluable for AFP response on C2D1 ($n \geq 15$).

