Genotype findings will be dichotomized as presence or absence of any mTOR pathway aberration or combination thereof (e.g. mutations in AKT, mTOR, PTEN, PIK3CA, and/or TSC1/2). This binary variable will be examined for its relationship with time to progression, overall survival, AFP response, and other clinical endpoints by univariate analysis using Cox's model. Concordance between primary and metastatic specimens on mutational profile will be described individually due to small sample size. Other tumor genotype findings and relationship to clinicopathologic covariates will be reported descriptively.

To optimize sample size and ensure adequate number of evaluable cases, these analyses of mTOR pathway IHC and genotype markers will also be performed on cases and samples CC#09455 when available, to ensure at least 25 evaluable cases with adequate archival tumor for testing. Although pooling of data and specimens across studies introduces potential confounding, it is appropriate for these exploratory analyses as the eligibility criteria and protocol therapy were overlapping for CC#09455 and the current study.

- Hepatitis B viral load: In all patients with active HBV infection, changes in HBV DNA quantitative by PCR (conversion from undetectable at baseline to detectable on study or an increase by $\geq 50\%$ from baseline versus unchanged from baseline) will be characterized using descriptive statistics (mean, median, standard deviation, and 95% confidence interval) to calculate the proportion of patients with an increase in viral load while on protocol therapy.
- Future biomarker research on banked specimens will be reported outside of the main study report

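### Section 9.4.4 pools CC#09455 cases into the exploratory mTOR marker analyses without a study term, and applies Cox's model to AFP response, which has no event time

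*Combined protocol and SAP*

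**What the plan says.** Section 9.4.4 plans two sets of mTOR analyses on archival tumour: IHC markers dichotomised at published cutpoints, and a yes/no genotype variable for any pathway aberration.

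- **IHC and TTP:** "Univariate analysis using Cox's model will be performed to test whether the dichotomized expression of each protein" predicts TTP, with hazard ratios and 95% intervals.
- **IHC and AFP:** the association with AFP decline at Cycle 2 Day 1 (by at least 50%, or at least 20%) "will be tested using Fisher's exact test".
- **Genotype:** the variable is examined for its "relationship with time to progression, overall survival, AFP response, and other clinical endpoints by univariate analysis using Cox's model".
- **Pooling:** to reach enough evaluable cases, "these analyses of mTOR pathway IHC and genotype markers will also be performed on cases and samples CC#09455 when available". The plan adds: "Although pooling of data and specimens across studies introduces potential confounding", but accepts it because "it is appropriate for these exploratory analyses as the eligibility criteria and protocol therapy were overlapping for CC#09455 and the current study".

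No study stratum, dose covariate, by-study result or analysis restricted to this trial is specified. The same section says the sample is too small to test TTP, OS or other clinical endpoints by pathway status. Only the AFP comparison is given a power figure.

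**The concern.** The plan names a confounder and then does not handle it. The documents do not say what CC#09455 is. The only predecessor they describe is the phase I trial of the same combination (Section 1.2.3.1). Section 1.3 calls that trial dose-finding, and Section 9.2.2 contrasts the present trial as having "no requirement for delays for dose escalation and frequent amendments which were associated with the Phase I study". Section 1.2.3.2 reports "The AUC of single-agent temsirolimus prior to addition of sorafenib in this cohort", so at least its PK patients began on temsirolimus alone. That section also reports faster temsirolimus clearance once sorafenib was added (5.86 v 4.37 L/h). In the present trial both drugs start on Cycle 1 Day 1 at one starting dose (Section 5.1). Cycle 2 Day 1 AFP would be the endpoint most sensitive to a different first cycle.

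Marker prevalence might differ too. This trial requires histological diagnosis (Section 3.3.1), while CC#09455 samples enter only as available. If outcome and prevalence both differ by study, an unstratified hazard ratio or odds ratio mixes the study contrast into the marker contrast. These are the only analyses serving the Section 2.3 objective of relating mTOR activation to outcome.

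The Cox model for AFP response is a separate defect that needs no assumption. Section 9.1.3 defines AFP response as a percent change and a proportion with at least 50% decline. No time to AFP response is defined anywhere.

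**Working it through.** **1. The plan's power figure.** Inputs from 9.4.4: 10% of 7 v 80% of 8 patients, two-sided alpha 10%. Both groups are labelled marker-low; I read one as marker-high. Enumerating Binomial(7, 0.10) and Binomial(8, 0.80), and rejecting when the one-sided Fisher p is at most 0.05 in either tail, gives 81.4%, which reproduces the stated 81%. The minimum-likelihood two-sided version gives 83.7%.

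**2. Share from CC#09455.** Expected IHC cases are 40-45 (9.4.4), this trial's maximum is 28 (3.2), and the phase I trial had 25 patients (9.2.2).

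- Minimum: 40 − 28 = 12, and 12/40 = 30%; 45 − 28 = 17, and 17/45 = 38%.
- Maximum, if CC#09455 is the phase I trial and all its patients contribute: 25/40 = 62.5%.

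The minimum assumes that every enrolled patient here yields IHC-quality tissue.

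**3. Evaluable numbers.** At 75% for TTP, 0.75 × 40 = 30 and 0.75 × 45 = 33.75, so about 30-34. At 60% for AFP, 24-27.

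**4. Cox false-positive rate with no marker effect, nominal 5%.** The documents give no between-study hazard ratio or prevalence by study; all of these are assumed. Two simulations were run. One used 42 cases (20 + 22, Wald test, 1,500 datasets, Monte Carlo SE √(0.05 × 0.95/1500) ≈ 0.6 points). The other used 32 cases (19 + 13, log-rank score test), which fits step 3.

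| Prevalence | Study HR | 42: unstratified | 42: stratified | 32: unstratified | 32: stratified |
|---|---|---|---|---|---|
| 50% v 50% | 1.5 to 2 | not run | not run | 5.8-5.9% | 5.8-5.9% |
| 40% v 60% | 1.5 | 5.0% | 4.3% | 7.1% | 6.2% |
| 40% v 60% | 2 | 6.4% | 5.2% | 7.6% | 6.6% |
| 30% v 70% | 1.5 | 7.8% | 4.7% | 8.7% | 5.7% |
| 30% v 70% | 2 | 11.7% | 4.7% | 11.4% | 5.2% |

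With no study difference at all (study HR 1), the 32-case unstratified test already runs at 5.6-6.4%, so the excess at 40% v 60% is about one point. The large-sample spurious marker HR is 1.06 (study HR 1.5) and 1.13 (study HR 2) at 40% v 60%, and 1.17 and 1.28 at 30% v 70%.

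**5. Fisher test of AFP decline, nominal 10%, 15 + 11 cases.** Without confounding its actual size is about 5.4%.

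- 40% v 60% prevalence: about 6% with AFP decline 30% v 50% by study, and about 8% with 20% v 60%.
- 30% v 70% prevalence: 7.6% with decline 30% v 50%, and 14.5% with 20% v 60%.
- The study-stratified exact test stays at 5.4-6.2% throughout.

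In the extreme case the pooled AFP decline rates are:

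- marker-high: (15 × 0.3 × 0.2 + 11 × 0.7 × 0.6)/(15 × 0.3 + 11 × 0.7) = 5.52/12.2 = 0.452
- marker-low: (15 × 0.7 × 0.2 + 11 × 0.3 × 0.6)/(15 × 0.7 + 11 × 0.3) = 4.08/13.8 = 0.296

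This is an odds ratio of about 2.0 with no marker effect.

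**6. Cost of stratifying the AFP test (10% v 80%).** Power goes from 84.1% to 80.5% with 15 cases, and from 98.0% to 97.8% with 26.

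**The case against.** The plan discloses the confounding in the same sentence that permits pooling, labels the analyses exploratory, and says the sample cannot support tests of TTP or OS. Several facts also favour comparability. The phase I trial was run at the same two institutions (1.2.3.1) with similar eligibility (9.2.2). IHC goes to one core with one reader (7.3.2) and uses published cutpoints. The markers come from archival tumour, so study dose cannot alter them.

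A reader might infer that CC#09455 patients as a group had a different exposure. The documents do not establish this. Its identity is an inference, Section 1.2.3.2 describes a 10 mg temsirolimus dose for the PK data, and a temsirolimus-alone start is documented only for patients with PK data. How many phase I patients received other doses is not stated.

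These points stand and limit the size of the problem. They do not remove it. Acknowledging a confounder is not adjusting for it, and the plan still tests each protein as a predictor of TTP and reports a hazard ratio with its interval. Nor do they touch the AFP model error.

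**Conclusion.** The concern holds in a limited form. A substantial share of the pooled cases, at least 30-38% of the expected number, comes from a study the documents do not identify, and no planned test accounts for study. Bias arises only if marker prevalence and outcome both differ by study; the documents give figures for neither. Under the assumed differences, inflation of the Cox test is small at 40% v 60% prevalence and moderate at 30% v 70%. The Fisher test exceeds its nominal 10% only in the most extreme setting tried. It would therefore be wrong to conclude that the pooled marker estimates are biased; they are unprotected against a bias that is cheap to prevent.

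A reader might also infer that these results will decide patient selection in a later trial. The documents do not say so: Section 1.4 speaks only generally of markers informing trial design, and the stated trigger for a randomised study is median TTP (Sections 1.3 and 9.2.1).

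The use of Cox's model for AFP response is an error as written, whatever the facts about CC#09455. The primary endpoint is unaffected. Overall this is a minor-to-moderate improvement.

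**What to change.** In Section 9.4.4:

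1. State what CC#09455 is, and its dose levels and start of each drug.
2. Stratify every pooled Cox analysis by study, with separate baseline hazards.
3. Test AFP response, for IHC and genotype alike, with an exact test stratified by study. This replaces Cox's model in the genotype paragraph and the unstratified Fisher test for IHC.
4. Report the estimate from this trial's patients beside the pooled one.

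This is a change of wording and a few lines of code; the study each case came from is already known, and no new data are needed. The downside is slightly wider intervals and about 0-4 points less power for the AFP test. The 81% figure should be recalculated for the stratified test.

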3.3.1 Inclusion Criteria

1. Patients must have histologically diagnosed AJCC stage II, III, or IV HCC not eligible for curative resection, transplantation, or ablative therapies
 - a. Cases with mixed, composite, or combined HCC-cholangiocarcinoma histology are eligible with approval from study chair and provided the treating investigator believes it is in the best interest of the patient to treat the tumor with therapy targeted towards the HCC component of tumor based upon review of pathology and clinical characteristics
2. Radiographically measurable disease by RECIST version 1.1 in at least one site not previously treated with chemoembolization, radioembolization, or other local ablative procedures (i.e. must have at least one measurable target lesion, either within the liver or in a measurable metastatic site); a new area of tumor progression within or adjacent to a previously-treated lesion, if clearly measurable by a Radiologist, is acceptable
3. No prior systemic cytotoxic chemotherapy or targeted therapy (including sorafenib) for HCC
4. Prior chemoembolization, local ablative therapies, or hepatic resection permitted if completed ≥ 4 weeks prior to study enrollment if patient has recovered with \leq grade 1 toxicity and if measurable disease (criterion 2) is present
5. Prior radiation for bone or brain metastases is permitted if patient is now asymptomatic and has completed all radiation and steroid therapy (if applicable) for brain or bone metastases ≥ 2 weeks prior to study enrollment.
6. Age ≥ 18 years.
7. Child-Pugh score of A or B with ≤ 7 points and meeting laboratory eligibility for all parameters
8. ECOG performance status of 0 or 1
9. Life expectancy greater than 3 months
10. Treatment with appropriate antiviral therapy for patients with active HBV infection is required
11. Treatment for clinically-significant hyperglycemia, hyperlipidemia, or hypertension that develops on study is required
12. Baseline blood pressure must be adequately controlled with or without antihypertensive medications prior to enrollment (systolic ≤ 150 mm Hg, diastolic ≤ 90 mm Hg)
13. Baseline cholesterol must be < 350 mg/dL and triglycerides < 300 mg/dL (with or without the use of antihyperlipidemic medications)
14. Baseline fasting blood glucose must be ≤ 140 mg/dL and hemoglobin A1c less than 7.5% (with or without the use of anti-diabetic medications)
15. Adequate baseline organ and marrow function as defined below

Adequate bone marrow function:

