6.1.1 Pretreatment Period

Patients with hypertension, diabetes mellitus, hyperlipidemia, and/or hepatitis B virus infection require optimization of these conditions prior to starting protocol therapy if found eligible upon screening.

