- Confirmation of antiviral therapy with an appropriate antiviral agent for HBV is required in patients with positive hepatitis B surface antigen, HBcAb IgM, and/or viral load - appropriate first line agents include entecavir, tenofovir, and lamivudine (note that lamivudine has higher resistance rates)
- Patients with a positive HBV viral load, HBcAb IgM, and/or HBsAg should be referred to a hepatologist if not already under the care of a hepatologist
- Initiate standing phosphate repletion for patients with baseline \geq Grade 2 hypophosphatemia – see *Section 5.3.1 Dose Modification and Dosing Delays*
- Confirmation of adequate blood pressure control with agents compatible with study drugs – see *Sections 5.3.1 and 6.7 and Appendices 6-9 Prohibited Medications*
- Serum or urine pregnancy test for women of childbearing potential within 14 days from start of study prior to the start of study drug

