* Patients will be followed every 3-6 months for up to 5 years after study discontinuation or until death, at standard-of-care clinic visits with treating investigator or by telephone calls from treating investigator or a designated study coordinator (± 3 months)

¹ May start study prior to obtaining specimens if pathology report is available

² Confirmation of antiviral therapy with an appropriate antiviral agent for HBV is required in patients with positive hepatitis B surface antigen, HBcAb IgM, and/or viral load

³ Sorafenib will be taken orally twice daily at starting dose with modifications per Section 5.2.3

⁴ Weight and vital signs on Days 8, 15, 22 of Cycle 2 and future cycles

⁵ Disease assessment including Child-Pugh, BCLC, and CLIP scores

⁶ Evaluation of clinical response or deterioration at Follow-Up Visit: overall survival will be measured from time of first dose of therapy to date of death, evaluation of any residual symptomatic adverse events (if applicable), other anti-cancer therapies

⁷ Complete metabolic panel (electrolytes, BUN, creatinine, glucose, calcium, magnesium, phosphorus, total and direct bilirubin, alkaline phosphatase, albumin, AST, and ALT)

⁸ Prothrombin time/ international normalized ratio (PT/INR)

⁹ Hepatitis B viral DNA quantitative in patients with positive hepatitis B viral load at baseline (Screening) and/or positive HBsAg, HBcAb total, and/or HBcAb IgM (odd cycles only or more frequently at investigator's discretion), and end of treatment if not measured within 4 weeks prior.

¹⁰ Screening and Day 1 of odd cycles only (Cycle 3, 5, 7, etc.)

¹¹ Initiate standing phosphate repletion for patients with baseline ≥ Grade 2 hypophosphatemia; adjust dosage as clinically indicated at each visit

¹² CTC on Day 1 of Cycles 1, 2 & 3 only. See Study Laboratory and Procedures Manual for instructions

¹³ Banking blood samples on Cycle 1 Day 1, Cycle 1 Day 8, and Cycle 3 Day 1, and at End of Treatment (if not done within 4 wks). See Study Laboratory and Procedures Manual for instructions

¹⁴ Odd cycles only, every 8 weeks ± 7 days, starting Cycle 3, Day 1

¹⁵ If not done within 8 weeks, imaging with CT chest (with or without contrast) plus triphasic CT abdomen and pelvis with intravenous contrast or triphasic gadolinium-enhanced MRI abdomen/pelvis

¹⁶ May use values from >28 days from registration

¹⁷ Temsirolimus infusion may be performed within ± 3 days

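### For patients with detectable HBV DNA at screening, section 9.4.4 scores change only against the screening load, so a large rebound after suppression is classed as unchanged while a 1.5-fold rise counts as an increase

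*Combined protocol and SAP*

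**What the plan says.** The hepatitis B item of section 9.4.4 has two ways to count an increase: "conversion from undetectable at baseline to detectable on study or an increase by" at least 50%. The only alternative it names follows directly: "from baseline versus unchanged from baseline". The stated aim is "to calculate the proportion of patients with an increase in viral load while on protocol therapy".

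The reference value is the screening sample, drawn within 28 days of Day 1 (section 6.1.1.1). Footnote 9 of Table 6.1 ties baseline to it: "Hepatitis B viral DNA quantitative in patients with positive hepatitis B viral load at baseline (Screening". Table 6.1 shows no HBV DNA test in Cycle 1. Later tests fall on odd cycles, or more often at the investigator's discretion, and at end of treatment if none was done in the preceding 4 weeks.

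Three places bear on how the load may move after that sample:
- Section 3.3.1: "Treatment with appropriate antiviral therapy for patients with active HBV infection is required".
- Section 6.1.1.1: "Confirmation of antiviral therapy with an appropriate antiviral agent for HBV is required in patients with positive hepatitis B surface antigen"; the same line extends this to patients with positive core IgM or a positive viral load.
- Section 6.1.1: patients with hepatitis B, among other conditions, "require optimization of these conditions prior to starting protocol therapy if found eligible upon screening".

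No minimum time on antivirals and no ceiling on the screening load is stated.

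**The concern.** The protocol monitors HBV because mTOR inhibition may be immunosuppressive (section 1.4.4), and sections 2.4.3 and 9.1.4 promise rates of viremia or reactivation. The event of interest is virus returning after control. For a patient detectable at screening, the rule compares each later load with a value that may predate control by antivirals. It has no reference to the lowest load reached, no log10 threshold and no class for a fall.

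The reported proportion can therefore be too low, because rebounds are missed, and too high, because small rises are counted. With 25 evaluable and at most 28 enrolled patients, one misclassified patient moves it by at least 1/28, or 3.6 percentage points, and by more within an HBV subset.

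**Working it through.** The plan attaches no expected rate, sample size or power to this endpoint, so there is no stated figure to reproduce. The check applies the rule literally.

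**1. The threshold.** A 50% rise is a factor of 1.5, and log10(1.5) = 0.176.

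**2. Rebound needed after a fall.** If the load falls by d log10 from screening, it must rise 1.5 × 10^d-fold from its lowest value to count: 150-fold for d = 2 and 1,500-fold for d = 3.

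**3. Illustrative courses** (IU/mL; detection limit of 20 assumed):

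| Screening → lowest → later | Later ÷ screening | Later ÷ lowest | Rule as written | Rise of at least 1 log10 over lowest |
|---|---|---|---|---|
| 1,000,000 → 100 → 100,000 | 0.1 | 1,000 (3.0 log10) | unchanged | increase |
| 1,000,000 → 100 → 1,400,000 | 1.4 | 14,000 (4.15 log10) | unchanged | increase |
| 100,000 → undetectable → 10,000 | 0.1 | at least 500 (2.7 log10) | unchanged | increase |
| 1,000,000 → 100 → 1,600,000 | 1.6 | 16,000 (4.2 log10) | increase | increase |
| undetectable → undetectable → 10,000 | – | at least 500 (2.7 log10) | increase (conversion) | increase |
| 100 → 150 | 1.5 | 1.5 (0.18 log10) | increase | not counted |

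The third course is not rescued by the conversion limb, which requires an undetectable value at baseline. A fall of 3 log10 with no rebound is also unchanged.

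**4. Constant true load, well above the detection limit.** Take independent normal errors on log10 values. The SD is assumed, since the documents give none. For one follow-up test, P = 1 − Φ(0.176 / (SD × √2)):
- SD 0.1: 1 − Φ(1.245) = 0.107
- SD 0.2: 1 − Φ(0.623) = 0.267
- SD 0.3: 1 − Φ(0.415) = 0.339

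For several tests against one baseline, by simulation:

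| Rule | Tests | SD 0.1 | SD 0.2 | SD 0.3 |
|---|---|---|---|---|
| As written | 1 | 11% | 27% | 34% |
| As written | 3 | 23% | 49% | 58% |
| As written | 6 | 34% | 62% | 71% |
| At least 1 log10 over lowest earlier value | 6 | 0.0% | 0.4% | 13% |

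Three tests correspond to Cycles 3, 5 and 7, roughly six months.

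**5. Constant true load exactly at the detection limit, three follow-up tests.**
- The rule as written counts 45%, 53% or 58% at SD 0.1, 0.2 or 0.3.
- Extending plain conversion to any undetectable on-study value would be worse. Each of the four samples is detectable with probability 1/2. Only 5 of the 16 patterns have no undetectable value before a detectable one, so 1 − 5/16 = 69% would be counted.
- A rise of at least 1 log10, with undetectable values set to the limit, counts 0.1% or fewer.

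**The case against.** The case for leaving the rule alone has several sound parts.

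- **Scope.** A reader might infer that rebounds in suppressed patients are missed generally. They are not. Anyone undetectable at screening is counted on any conversion, and any rebound reaching 1.5 times screening is counted. Confirming antiviral therapy is itself a screening step, so the documents allow a post-screening fall without showing that it is common. The number of such patients could be zero.
- **Noise.** The documents give no assay, SD or detection limit. The percentages are a range under assumptions and apply to quantifiable, stable loads. That a 1.5-fold change counts needs no assumption.
- **Other summaries.** Section 9.4.4 also lists mean, median, SD and a 95% confidence interval, so falls and sizes of change enter somewhere. These need not reveal an individual rebound.
- **Increase is not reactivation.** Section 9.4.4 scores an increase, and the Abstract names increase and reactivation side by side. The 50% cut should not be read as a stated definition of reactivation. However, no other numerical definition appears, so this score is the only defined quantity behind the promised rate.
- **Patient safety.** A reader might infer that reactivation would go unnoticed in patients. The documents do not support that. HBV DNA is repeated, liver tests are weekly, hepatology referral is specified, and section 6.1.5 makes a stable or undetectable load a condition for ending follow-up. None of this depends on the score.

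These points narrow the finding and lower its weight. They do not change how the rule classifies the first three courses in the table.

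**Conclusion.** The point holds for patients with detectable HBV DNA at screening whose load then falls. For them, a rebound of 100- to 1,000-fold or more from the lowest value is scored unchanged if it ends below 1.5 times screening, and a large fall is scored unchanged as well. In anyone with a detectable screening load, a rise of 0.18 log10 is scored as an increase. These statements follow from the text alone.

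Two things rest on assumption: the illustrative courses, including the detection limit of 20 IU/mL, and the rates of 11% to 34% (one test) and 23% to 58% (three tests), which need a per-sample SD of 0.1 to 0.3 log10. The number of patients affected is not known.

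The endpoint is exploratory and descriptive, with no test, decision or stopping rule attached. The primary analysis, sample size and patient monitoring are unaffected. This is a minor correction.

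**What to change.** In section 9.4.4:
1. Analyse log10 HBV DNA. Score an increase as a preset rise clearly beyond assay noise, for example at least 1 log10, above the lowest earlier value (screening or on study), with undetectable values set to the assay's detection limit. The threshold is an example; it should be set from the precision of the assay in use.
2. Keep the existing category of undetectable at screening becoming detectable, but report it separately, since it is noisy for loads near the limit. Do not extend plain conversion to undetectable on-study values; there, only the preset rise should count.
3. Add a decrease class, as section 9.4.3 does for AFP.
4. Report each proportion with an exact binomial 95% confidence interval.
5. The 50% rule may stay as a description.

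The cost is wording only, with the same samples and no change to patient management. Rises of 1.5- to 10-fold would be described rather than counted. At an SD of 0.3 with six tests, about 13% of patients with a constant load would still be counted, against 71% under the present rule.
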